# 6.2.4 Integrative Sessions 24 Hours after Experimental Session [Visits 6, 10, 15 (15 for full dose group only)]

On the morning after the MDMA session, the participant will meet with both investigators during a 90-minute integrative psychotherapy session.

Adherence criteria for integrative sessions should be completed as a part of one of the three sessions following each experimental session. These elements do not have to be accomplished in any specific order or all in each and every integrative session. Generally, adherence criteria for these sessions include discussing material that emerged during experimental sessions and helping participants integrate their experiences both internally and into daily life. Therapists will emphasize their commitment to support the subject during the integration period and will be available via phone or pager. Subjects will be encouraged to relax and rest as much as possible for several days after the experimental session.

Participants will complete the C-SSRS during each integrative session. At the beginning of this session, the participant and both investigators conducting psychotherapy will indicate their beliefs concerning participant condition assignment. The participant and investigator will then discuss and review events, thoughts, feelings and memories that occurred during the experimental session. If necessary, the investigators will help the participant to reduce any residual psychological distress he or she may be experiencing. The therapists will also encourage exploration of any new insights and perspectives resulting from states of acceptance, feelings of intimacy, and reduced fear that may have occurred during MDMA sessions and that may be applicable to emotionally distressing

situations in everyday life. The investigators will be supportive, validating the MDMA experience and facilitating understanding and emotional clearing. The investigators will assess participant mental health and the presence of any remaining reactions during integrative psychotherapy sessions. Integrative psychotherapy sessions can also serve as an opportunity for the investigators to gather information in an unstructured manner about the effects of MDMA on the participant. If subjects who have pre-existing tinnitus or chronic pain mention any changes, the visual analog scale will be used to collect the changes in symptoms.

After this psychotherapy session, a person previously selected by the subject will provide a ride home. If the participant is unable to locate an individual to take him or her home, the investigators will arrange an alternative means of transportation. The entire integrative psychotherapy session may be recorded to audio and video. Participants may receive copies of this session upon request. Therapists will be accessible if the participant needs support outside the scheduled integration sessions.

Adverse Events and medications will be collected as described in Sections 8 and 9 of the protocol.

# 6.2.5 Daily Telephone Contact for Seven days after an Experimental Session

Investigators will follow the most recent version of the Treatment Manual in all matters relating to follow-up subsequent to the experimental psychotherapy sessions. Starting on the day of the non-drug integrative psychotherapy session following each experimental session, one of the investigators will contact the participant via telephone daily for one week. The telephone contact will be for a brief check-in lasting 5 to 15 minutes, or as long as necessary to address any participant's concerns or difficulties integrating their experience and to assess participant well-being. Additional telephone contact can be initiated at the request of the investigators or participant. On the second and seventh day of telephone contact, the C-SSRS will be administered to monitor for suicide risk.

Adverse Events and medications will be collected as described in Sections 8 and 9 of the protocol.

If the investigators are unable to reach a subject by telephone despite repeated attempts, every effort will be made to contact their outside physician or a family member to be sure they receive any support needed. If the investigators eventually contact the person, this participant would be permitted to remain enrolled in the study only if measures could be put in place to assure that such a problem would not recur.

#### 6.2.6 Integrative Psychotherapy between Experimental Sessions

In addition to the session the morning after each experimental session, the subject will have two additional integrative psychotherapy sessions with the therapists lasting 90 minutes between experimental sessions and in the month following the last experimental session in each stage. The therapists may conduct more sessions if they and the subject deem it necessary. (See Time and Events Table). The purpose of these sessions is to

PS Study # MP8 39

provide continued support for the participant as she or he considers his or her experiences during the experimental sessions and strives to integrate them into their lives. If subjects who have pre-existing tinnitus or chronic pain mention any changes, the visual analog scale will be used to collect the changes in symptoms.

Adherence criteria for integrative sessions should be completed as a part of one of the three sessions following each experimental session. These elements do not have to be accomplished in any specific order or all in each and every integrative session. Generally, adherence criteria for these sessions include integration of material that emerged as a part of experimental sessions and afterward into daily life. Therapists will validate the choices of the subject to communicate or not on these thoughts, feelings and experiences. Therapists will emphasize their commitment to support the subject during the integration period and will be available via phone or pager. Subjects will be encouraged to relax and rest as much as possible for several days after the experimental session.

The investigators will use clinical judgment to assess the participant's psychological well-being during this period of time. Suicidality will be assessed with the C-SSRS. Each integrative session may be recorded to audio and video, and participants may receive a copy of one or more integrative sessions upon request. If there are any indications of continuing anxiety or distress, the investigators may arrange to address it in a specially scheduled additional non-drug therapy session, through continuing telephone contact, or at the next regularly scheduled non-drug therapy session. The participant may also initiate contact with the investigators at any time throughout the study.

Adverse Events and medications will be collected as described in Sections 8 and 9 of the protocol.

If an integrative session falls within the seven-day period of telephone contact, it will replace the day of telephone contact, and spontaneously reported reactions will be recorded as reported during the session.

## 6.2.7 Evaluation at Primary Endpoint & Unblinding (Visit 13)

The primary endpoint evaluation in Stage 1 will occur one month after the second blinded experimental session. This visit will consist of two meetings that may be completed on separate days, one with the independent rater and the other with the therapists. The blinded independent rater will administer: CAPS to assess PTSD symptoms, BDI-II to assess depression symptoms, GAF to assess general psychological function, PTGI to assess post-traumatic growth (in reference to start of the study), PSQI to assess sleep quality, DES-II to assess dissociation symptoms and NEO PI to assess personality. The blinded independent rater will provide their belief of the subject's condition assignment.

After completing all assessments and measures with the independent rater, the subject will meet with the therapists for approximately 30 minutes. Following the visit with the independent rater the blind will be broken for the subject's condition assignment. The independent rater will remain blind to condition assignment at this time. The therapists will assess suicidality with the C-SSRS. The visual analog scale will be used to collect

changes in subjects who have pre-existing tinnitus and chronic pain symptoms.

If the subject had been assigned to receive medium dose or low dose MDMA, the therapists will discuss continuation to Stage 2. Low and medium dose subjects will not complete the third experimental session and associated integrative sessions in Stage 1. Participants who decline continuing to Stage 2 will complete the Responses to Research Participation Questionnaire (RRPQ). If participants had been assigned to the full dose condition in Stage I, they will provide their perceptions of experimental sessions at this point. The therapists will discuss scheduling the third open label full dose experimental session and integrative sessions.

Adverse Events and medications will be collected as described in Sections 8 and 9 of the protocol.

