### 12.0 Data Analysis

The Sponsor will judge the clinical and statistical significance of the study and estimate effect size and statistical power based on a comparison of observer-blind data collected at baseline and the primary endpoint using the primary outcome measure, which is the CAPS.

The sample selection is expected to produce acceptably homogeneous groups due to their diagnosis of with PTSD with CAPS scores of at least 50 who have not responded to treatment. There is no expectation that conditions will differ significantly in composition by gender, race or ethnicity, duration of PTSD diagnosis or presence versus absence of other permitted psychiatric disorders, as depression.

The sponsor will examine individual CAPS, BDI-II, PTGI, PSQI, DES-II and GAF scores at baseline and the primary endpoint, in low dose, medium dose and full dose conditions. Descriptive statistics will be calculated for all measurements overall and by condition. Distributional characteristics will be examined for outliers and extreme values and, if either is evident. If outliers are found in primary or secondary outcome measures, the sponsor will perform analyses with and without the outlying data. Effect sizes for all outcome measures for primary endpoint, Stage 1, secondary endpoint, end of Stage 2, and 12-month follow-up will be estimated using Cohen's techniques.

All analyses of data from the primary endpoint will contain blinded data. Analysis of variance will be used to compare Global CAPS scores by dose condition at the primary endpoint.

Analysis of variance, or nonparametric analysis if assumptions are not met, will be used to compare the dose conditions for change in BDI-II, PTGI, PSQI, GAF, DES-II and NEO PI scores separately. If scores cannot be examined sufficiently in this model, then analyses will compare available data through the use of difference scores.

The sponsor will examine open-label data collected two months after the third Stage 1 experimental session. The sponsor will perform a within-subject analysis of full dose participants.

Subjects who discontinue treatment prior to the primary endpoint will be asked to complete an outcome assessment prior to continuing to the long-term follow-up. The data from these subjects will be tested for equivalence to data from subjects completing the study per protocol. If found to be equivalent, data from these subjects will be presented as

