### Columbia Suicide Severity Rating Scale (C-SSRS)

Suicidal ideation and behavior will be summarized according to suggestions made in the Columbia-Suicide Severity Rating Scale Scoring and Data Analysis Guide [3]. A positive response for suicidal ideation is counted when a subject answers "yes" to any one of the five suicidal ideation questions (Categories 1-5) on the C-SSRS, i.e. a score > 0 for suicidal ideation score. Serious suicidal ideation is a suicidal ideation score of 4 or 5. A positive response for suicidal behavior occurs when a subject answers "yes" to any one of the five suicidal behavior questions (Categories 6-10) on the C-SSRS, i.e. a score > 0 for suicidal behavior score. The number and percent of positive responses of Positive Ideation, Serious Ideation, and Positive Behavior will be tabulated by treatment group and time period. P-values will be calculated using the chi-squared test for overall treatment group differences and Fisher's exact test will be used for pairwise testing. Compare lifetime serious suicidal ideation and positive behavior frequencies to cumulative frequencies anytime during the study until end of stage 1 and stage 2 using chi-squared test for overall treatment group differences and Fisher's exact test for pairwise testing.

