### Visual analog scale for Tinnitus and/or Pain visual analog scale

Formal analysis of Changes in Tinnitus and/or Pain visual analog scale scores will only occur if three or more subjects complete Changes in Tinnitus and/or Pain visual analog scale at baseline and primary endpoint. Likewise, formal between-groups analyses will not be performed if all primary endpoint scores are from subjects assigned to the same condition. T-tests will be performed on the difference between baseline and primary endpoint Changes in Tinnitus and/or Pain visual analog scale scores in the full dose and comparator dose conditions, with p set at 0.05. If the only scores available are for subjects in a single condition, then a paired t-test will be performed comparing baseline and primary endpoint Changes in Tinnitus and/or Pain visual analog scale scores, with p set at 0.05.

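### As written, Protocol 6.2.7 opens the code at V13 before the therapists' C-SSRS and the tinnitus/pain VAS, so two safety measures compared between dose groups may be collected unblinded

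*Protocol*

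**What the plan says.** Protocol 6.2.7 describes V13 as follows: "This visit will consist of two meetings that may be completed on separate days, one with the independent rater and the other with the therapists". In the first meeting, the rater collects the CAPS, BDI-II, GAF, PTGI, PSQI, DES-II and NEO PI and records a guess of the assignment. The subject then meets the therapists. On the blind, the section says: "Following the visit with the independent rater the blind will be broken for the subject's condition assignment". It adds: "The independent rater will remain blind to condition assignment at this time". The next sentence is "The therapists will assess suicidality with the C-SSRS". The tinnitus/pain scale follows ("The visual analog scale will be used to collect" changes in subjects with these conditions), and then the discussion of Stage 2 or the third session.

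Protocol Table 3 and the Stage 1 table in SAP 4.1 mark C-SSRS, VAS and unblinding at V13 without an order.

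Three other places describe the blind more generally. Protocol 5.0 and SAP 4.0 break it once the subject has completed the primary endpoint evaluation. Protocol 5.2 keeps it through the primary endpoint assessment, except in an emergency. Protocol 12.0 says: "All analyses of data from the primary endpoint will contain blinded data".

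SAP 8.9.4 compares both measures between groups. For the VAS: "T-tests will be performed on the difference between baseline and primary endpoint Changes in Tinnitus and/or Pain visual analog scale scores", full dose against comparator dose, provided that at least three subjects have both scores and that they do not all come from one condition. C-SSRS positive responses "will be tabulated by treatment group and time period", with a chi-squared test overall and Fisher's exact test pairwise. Cumulative frequencies to the end of each stage are also compared.

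**The concern.** The VAS is self-rated and the C-SSRS is an interview. Both can be moved by what the respondent has just been told, and the C-SSRS also by what the interviewer knows. If a subject learns the dose and is then asked about symptoms or suicidal thoughts, any reaction to the news is counted in the dose comparison. The two meetings may fall on separate days, so the news may have had time to act.

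For low- and medium-dose subjects V13 is the last scheduled C-SSRS of Stage 1, because footnote J of Table 3 takes them out of visits 14 to 18. Comparing suicidality between conditions is a stated safety objective (Protocol 3.3, SAP 3.3). The protocol takes trouble elsewhere to protect the blind: under 6.1.2, blood pressure and pulse printouts are sealed until the subject is unblinded. A loose order at V13 is out of keeping with that. Once a subject has been told the dose, a blinded V13 answer cannot be recovered.

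**Working it through.** **Order of events.** The documents give no figure to reproduce, so the main check sets the texts side by side.

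1. Protocol 6.2.7 makes the end of the rater meeting the trigger for unblinding, not the end of V13.
2. It names only the rater as staying blind. The rater collects neither the C-SSRS nor the VAS.
3. Both measures are listed after the unblinding sentence, and the C-SSRS is assigned to the therapists.
4. Protocol 5.0 and 5.2 and SAP 4.0 place unblinding after the primary endpoint evaluation. Both measures are scheduled at V13, so on that reading they come before the code is opened.
5. Protocol 6.1.3 fixes two other items relative to unblinding: the rater's guess before it and the perceptions measure after it. No section does this for the C-SSRS or the VAS.

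Points 1 to 3 and point 4 give opposite orders, and nothing in the documents says which governs.

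**Use of the data.** The VAS test names the primary endpoint. The C-SSRS test refers to time periods that the SAP does not list. V13 is a scheduled C-SSRS visit within Stage 1, so its responses feed the cumulative comparison and any time period that includes V13.

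**Illustration for the VAS.** The documents give neither a reporting shift nor the number of subjects with tinnitus or chronic pain, so both are assumed. Let b be a between-arm shift in SD units caused only by knowing the dose, with no true effect. The two-sided 0.05 t-test (level from SAP 8.0) rejects with probability P(|T| > c), where T is noncentral t with n1 + n2 − 2 degrees of freedom and noncentrality b / √(1/n1 + 1/n2). At 6 v 6 and b = 0.5 the noncentrality is 0.5 / √(1/6 + 1/6) = 0.866 and c = 2.228 on 10 degrees of freedom, which gives 0.123.

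| Subjects with VAS | b = 0.25 | b = 0.50 | b = 0.75 |
|---|---|---|---|
| 3 v 3 | 0.057 | 0.077 | 0.111 |
| 4 v 4 | 0.060 | 0.092 | 0.147 |
| 6 v 6 | 0.068 | 0.123 | 0.218 |
| 12 v 12 | 0.090 | 0.216 | 0.420 |

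The last row is an upper bound on sample size. It needs all 24 subjects (12 full dose, 6 + 6 comparator) to have tinnitus or chronic pain.

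**Illustration for the C-SSRS.** One reactive positive answer in a six-subject arm moves that arm's rate by 1/6, or 17 percentage points. Starting from no positives, this does not reach significance: Fisher p = 6/18 = 0.33 against 0/12 and 1.0 against 0/6. The overall chi-squared on 1/6, 0/6 and 0/12 is 3.13 on 2 degrees of freedom, p = 0.21.

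**The case against.** The strongest reply is that the order is inferred. Section 6.2.7 never says outright that the C-SSRS or VAS follows unblinding, and its sentences are not strictly chronological: the therapist meeting is mentioned before the sentence that breaks the blind. Where the protocol wants a measure after unblinding, it says so, as for the perceptions measure. Protocol 5.0 and 5.2 can be read as protecting all of V13. This stands as a limit on certainty. It does not remove the problem, because 6.2.7 is the section that sets out the visit and its trigger is the rater meeting.

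Other limits also stand:

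- Both are safety measures (SAP 7.2), and Protocol 6.1.2 calls the VAS exploratory. The VAS test is conditional, and the trial is a pilot meant to estimate effect sizes.
- The SAP does not name V13 for the C-SSRS, so a reader might infer a planned C-SSRS test at that visit, which the documents do not state.
- A reader might infer that the Protocol 12.0 statement on blinded data is plainly false. Read literally it conflicts with 6.2.7, but it stands directly before the CAPS analysis and may mean only the rater-collected outcomes.
- A reader might also infer a known direction, such as disappointment after a lower dose. The documents do not support that: the same meeting offers those subjects open-label treatment, which could offset it.
- A suicidality check after unblinding has a plausible safety role, so moving the only one earlier would lose something.

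**Conclusion.** The point holds as a conflict between sections with an avoidable risk of bias. Under 6.2.7 as written, the V13 C-SSRS and VAS may be collected when both subject and therapist know the dose, contrary to Protocol 5.0 and 5.2 and SAP 4.0. The VAS comparison at the primary endpoint is explicitly exposed when its conditions are met. The C-SSRS comparison is exposed through the by-period and cumulative analyses.

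Neither the direction nor the size of any bias can be derived from the documents. The range of about 7% to 22% at 6 v 6 rests wholly on assumed shifts of 0.25 to 0.75 SD and an assumed number of VAS subjects. A single reactive C-SSRS answer, starting from none, would not produce a significant result.

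The stronger conclusion, that the primary analysis is compromised, is not supported. CAPS and the other rater-meeting scales are collected before the code is opened. This is a change that should be made because it is cheap, not a flaw in the main result.

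**What to change.** - In Protocol 6.2.7, state that the V13 VAS and the C-SSRS used for between-arm comparison are completed before the code is opened. This reconciles the section with Protocol 5.0 and 5.2 and SAP 4.0.
- Add the same order as a footnote to the V13 column of Protocol Table 3 and of the Stage 1 table in SAP 4.1.
- Keep any suicidality check made after unblinding. Record it separately, report it as safety data, and leave it out of any V13 between-arm test.
- In SAP 8.9.4, list the C-SSRS time periods and say whether a post-unblinding response enters the cumulative comparison.
- For any subject already assessed after unblinding, label the V13 C-SSRS and VAS as unblinded in the SAP.

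The cost is one reordered paragraph, two footnotes and a few sentences in the SAP. The downside is a possible second short C-SSRS at V13.

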# 6.2.8 Evaluation Two Months after the Third Experimental Session (Visit 18-Full dose subjects only, End of Stage 1)

The final evaluation for full dose subjects in Stage 1 will occur two months after the third experimental session. Participants will meet the independent rater for 90 to 120 minutes. The independent rater will administer the CAPS, BDI-II, PTGI (in reference to the start of the study), DES-II and the PSQI. The independent rater will assess participants on the GAF. Administration of CAPS may be recorded to video.

After completing all assessments and measures at the evaluation at the end of Stage 1 with the independent rater, the full dose subjects will meet with the investigators for approximately one hour. The investigators will administer the C-SSRS, and the subjects will indicate their perceptions of a third experimental session. Subjects will complete the RRPQ. The visual analog scale will be used to collect changes in pre-existing tinnitus and chronic pain symptoms.

Subjects will receive a memory aid card for use between this visit and the 12-month follow up. Subjects will use this card to record AEs, medications and changes in psychiatric status that they will be asked about at the termination visit. Memory aids will not be collected. Subjects may return to taking psychiatric medications from this point onward if necessary.

# 6.2.9 Opportunity for Participants in Low Dose and Medium Dosage Condition to Enroll in Open-Label Study Segment ("Stage 2")

Low dose and medium dose participants who elect to enroll in Stage 2 will undergo a course of therapy and evaluation nearly identical to the full dose group in Stage 1, but given in an open-label context.

